Effectiveness of an Occupation-Based Intervention Compared with Therapeutic Exercise for
Older Adults with Shoulder Osteoarthritis: A Pilot Randomized Controlled Trial

NCT Number: Not Assigned

Document Date: 10/04/2019

Statistical Analysis Plan (SAP)

Method

Research Design and Participants

We conducted a single-center, parallel-group RCT in an outpatient clinic. Participants were recruited via convenience sampling from the assisted and independent living facility where the outpatient clinic was located. Inclusion criteria were diagnosis of shoulder osteoarthritis and ages 65 years or older. Diagnosis was confirmed by physician examination or radiographic imaging. Exclusion criteria were previous shoulder injuries, acute pathology, previous shoulder surgery, current use of pain medication, inflammatory arthritis, upper extremity neuropathy or myopathy, current participation in a home exercise program, or a score of <18 on the Mini-Mental State Examination (MMSE).

This study was approved by the Bay Path University Institutional Review Board. All participants gave written informed consent to participate. Eighteen older adults were recruited for the study, four did not meet the MMSE criteria, and two did not have a confirmed diagnosis of shoulder osteoarthritis. Two participants withdrew from the study prior to randomization. Computer-based randomization was used to allocate the remaining ten participants into two groups: the Ten participants ($N = 10$) were randomly allocated to the OBI + TE ($n = 5$) or the TE ($n = 5$) group.

Outcomes Measures

The Quick Disabilities of the Arm, Shoulder and Hand (QuickDASH) (Beaton, Wright, Katz, Upper Extremity Collaborative Group, 2005) questionnaire was the primary outcome measure and was used to assess the impact of the intervention on physical function and symptoms of shoulder osteoarthritis. Scores range from 0 to 100. A lower score indicates less disability. The Canadian Occupational Performance Measure (COPM) was used to determine the

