effect of the intervention on participants' self-perception of occupational performance and satisfaction over time (Law et al., 1990). Shoulder range of motion (ROM) was measured using a functional test established by Burner et al. (2014). Active abduction, flexion, external rotation, and internal rotation of the shoulder were assessed with participants seated on the edge of a mat with no back support and hips and knees at 90 degrees using a 3-point scale for ROM and pain (Burner et al., 2014). A Jamar hand dynamometer was used to measure the grip strength of the participants (che Daud et al., 2016). Pain was measured using the Numeric Pain Rating Scale (NPRS) (Hawker, Mian, Kendzerska, & French, 2011).

Procedure

Participants were randomly allocated using a computer-generated random number table. Outcome measures were administered prior to the intervention, a week after the conclusion of the intervention, and four weeks after the intervention ended. Protocols for occupation-based intervention for the treatment of upper extremity musculoskeletal disorders vary widely. According to a systematic review by Weinstock-Zlotnick & Mehta (2019), occupation-based interventions ranged from 2 to 10 weeks in duration, 1 to 5 sessions per week, with individual sessions lasting at least 30 minutes to a maximum of 3 hours. For this study, both groups were seen for 60-minute sessions, two times per week, for six weeks. The sessions for the OBI + TE group consisted of 30 minutes of TE followed by 30 minutes of OBI. The TE group sessions consisted of 60 minutes of TE. All participants received ten minutes of moist heat on the affected shoulder as a preparatory activity before the session started.

Control group. The TE protocol was completed systematically. Passive range of motion (PROM), active-assistive range of motion (AAROM), active range of motion (AROM), and

strengthening activities were completed sequentially. Participants were advised to respect and avoid pain with all exercises.

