Intervention group. COPM results were used to select client-centered occupations, collecting and placing items in cabinets, washing windows and tables, and hanging clothes on a clothesline, for the OBI intervention. To make the activities more meaningful and relevant, interventions were completed within a simulated home environment. Participants were encouraged to use the affected upper extremity as much as possible, but to respect pain. The same TE protocol as the control group was completed prior to OBI, but with fewer repetitions, as a preparatory activity for the OBI.

Data Analysis

Data was collected and stored in a secure and locked file cabinet to protect the confidentiality of the participants. Statistical analyses were conducted using IBM SPSS Statistics (Version 23.0; IBM Corp., Armonk, NY). Descriptive statistics for all continuous variables included mean, standard deviation, and range. Descriptive statistics for categorical variables included frequencies and percentages. Paired sample t-tests were completed for each group for both the one week and four week follow up assessments to determine the effectiveness of the treatment protocol over time. Three sets of paired t-tests were used to compare the groups to each other at baseline, one week posttreatment, and four weeks posttreatment. The statistical significance level was set at $p < 0.05$ (two-tailed).

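### The between-arm tests are written as paired although the arms are independent, they use no baseline value, and the baseline significance test corrects nothing

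*Combined protocol and SAP*

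**What the plan says.** Research Design and Participants describes the design: "We conducted a single-center, parallel-group RCT in an outpatient clinic". Ten participants "were randomly allocated to the OBI + TE ($n = 5$) or the TE ($n = 5$) group". Procedure adds: "Participants were randomly allocated using a computer-generated random number table". No matching or stratification is mentioned.

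Outcomes Measures says that the QuickDASH "questionnaire was the primary outcome measure". Procedure gives the timing: "Outcome measures were administered prior to the intervention, a week after the conclusion of the intervention, and four weeks after the intervention ended". A baseline value therefore exists for each outcome.

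Data Analysis names two families of tests, at a two-sided 5% level. Within arms: "Paired sample t-tests were completed for each group for both the one week and four week follow up assessments". Between arms: "Three sets of paired t-tests were used to compare the groups to each other at baseline, one week posttreatment, and four weeks posttreatment". It describes no between-arm comparison of change, no covariate adjustment, and no action that depends on the baseline test.

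**The concern.** Three faults sit in one sentence of the plan.

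- **Pairing.** A paired test needs a link between each person in one arm and one person in the other. Random allocation into parallel arms gives none. Run literally, the test would depend on the arbitrary order of the records and have 4 degrees of freedom instead of 8. If the word is a slip, the reader cannot tell which test was run.
- **Unused baseline.** The comparisons at one and four weeks rest on follow-up scores alone. The within-arm tests presumably use baseline, but they give no contrast between the arms.
- **Baseline significance test.** Under randomisation any baseline difference is due to chance, so the test answers no useful question. A significant result corrects nothing, and with five per arm a non-significant result is weak reassurance.

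At stake is the reading of this one allocation. If the arms start apart on QuickDASH, part of that gap passes into the follow-up comparison and can look like a treatment effect, or hide one.

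**Working it through.** **Inputs from the documents.** n = 5 per arm; independent arms; two-sided alpha 0.05; assessments at baseline, one week and four weeks. The plan gives no sample-size calculation, SD, effect size or correlation, so there is no figure of its own to reproduce.

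**Assumptions.** Normal scores with SD 1 at each time, all ten followed up, and a baseline to follow-up correlation ρ varied from 0 to 0.8. Results are in SD units. Items marked *sim* come from 1,000,000 simulated trials per setting, except ANCOVA power at ρ = 0 and 0.3 and power of the paired test, which come from 200,000.

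**1. Smallest baseline difference the test can flag.** This is t × √(2/5), in observed SDs.
- Independent, df 8: 2.306 × 0.632 = 1.46
- Paired, df 4, arbitrary pairs: 2.776 × 0.632 = 1.76

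**2. How often a large imbalance occurs and is missed.** P(|difference| > 1 SD) = 2 × P(Z > 1/0.632) = 0.114.
- Flagged (*sim*): 36% by the independent test, 29% by the paired test.
- Unflagged, as a share of all allocations: 0.114 × 0.64 = 7% and 0.114 × 0.71 = 8%.
- Measured in the *observed* SD instead, a difference of at least 1 occurs in 15.3% of allocations, and 0.05/0.153 = 33% are flagged. At 0.8 the figures are 24.2% and 0.05/0.242 = 21%. At about 1.18 the flagged share reaches 0.05/0.10 = 50%, so above that size the test no longer misses most imbalances.

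**3. Bias carried into follow-up.** Given a difference above 1 SD, its mean size is 0.632 × φ(1.58)/P(Z > 1.58) = 0.632 × 0.114/0.0569 = 1.27 SD. The unadjusted estimate carries ρ × 1.27, which is about 0.63, 0.76 and 0.89 SD at ρ = 0.5, 0.6 and 0.7. ANCOVA carries none.

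**4. Unadjusted independent t-test (df 8) against ANCOVA with own baseline (df 7)** (*sim*).

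| Assumed ρ | 0 | 0.3 | 0.5 | 0.6 | 0.7 |
|---|---|---|---|---|---|
| *Given baseline difference > 1 SD* | | | | | |
| False rejection, unadjusted | 5% | 8% | 12% | 15% | 19% |
| Root mean square error, unadjusted | 0.63 | 0.72 | 0.85 | 0.93 | 1.01 |
| Root mean square error, ANCOVA | 0.82 | 0.79 | 0.71 | 0.66 | 0.59 |
| Mean 95% CI half-width, ANCOVA (unadjusted 1.41) | 1.86 | 1.78 | 1.61 | 1.49 | 1.33 |
| *All allocations* | | | | | |
| Mean 95% CI half-width, ANCOVA (unadjusted 1.41) | 1.55 | 1.48 | 1.34 | 1.24 | 1.11 |
| Power for a 1 SD effect, ANCOVA (unadjusted 29%) | 25% | 27% | 32% | 36% | 44% |

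ANCOVA's false rejection rate is about 5%. The unadjusted test is conservative in the other 89% of allocations (4.1%, 3.7% and 3.2% at ρ = 0.5, 0.6 and 0.7), which restores 5% overall: at ρ = 0.5, 0.114 × 12% + 0.886 × 4.1% = 5.0%. Run as paired, false rejection given a difference above 1 SD is about 11%, 13% and 16%. Among only the imbalances that the independent baseline test fails to flag, the unadjusted rate is about 10%, 11% and 12%.

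**5. Break-even.** Two quantities cross near ρ = 0.4: half-width over all allocations, and root mean square error given a difference above 1 SD. Half-width given such a difference crosses later, near 0.65.

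**6. Cost of arbitrary pairing.** Mean half-width is t × E(s) × √(2/5), where E(s) is 0.969 with df 8 and 0.940 with df 4.
- Independent: 2.306 × 0.969 × 0.632 = 1.41
- Paired: 2.776 × 0.940 × 0.632 = 1.65

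Power for a 1 SD effect is 23% paired against 29% independent (*sim*).

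**The case against.** The strongest reply is that an unadjusted independent-groups comparison is valid after randomisation, so preferring ANCOVA with ten people does not correct an invalid test. This stands for overall type I error. The case for adjustment is conditional bias in the allocation obtained and, if ρ is high enough, precision.

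The benefit also depends on a correlation that the documents do not give. This stands too. At ρ of 0 to 0.3 ANCOVA has wider intervals and lower power, and at 0.5 power rises only from 29% to 32%. After a large imbalance its interval is usually the wider one at 0.5 and 0.6 (71% and 59% of such trials), though its estimate is unbiased.

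The 12% to 19% covers every difference above 1 SD, flagged or not. For the missed imbalances alone the rate is about 10% to 12%, which is milder but still about twice the nominal level. What counts as large is a choice, and the 1 SD cut uses the population SD, which this trial cannot observe.

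Finally, the pairing may be a slip of wording, and this is a pilot. A slip would still need correcting. Pilot status does not remove the point, because the title speaks of effectiveness, the plan sets a significance level, and chance imbalance is greatest in small samples.

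**Conclusion.** The concern holds. The between-arm test as written does not fit the design, the follow-up comparisons discard the baseline, and the baseline test neither corrects an imbalance nor reliably detects one of about 1 SD. These points follow from the text and from n = 5 per arm alone.

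The size of the gain from adjustment is less certain: it rests on an assumed ρ, normality and complete follow-up. At ρ of 0.5 to 0.7 ANCOVA removes a substantial bias in the 11% of allocations with a difference above 1 SD and improves average precision. Below about 0.4 it costs precision. Part of any gain over the plan as written, from 1.65 to 1.41 SD in half-width, comes simply from dropping the pairing. Either analysis remains imprecise with ten people. The plan should be changed, with both estimates shown.

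**What to change.** - State that the arms are compared as independent groups, and record which test was actually run.
- At each follow-up, report the between-arm difference by ANCOVA with a 95% CI, with group as the factor and that outcome's own baseline as the only covariate. Take QuickDASH first, then COPM performance, COPM satisfaction, grip strength and pain rating. The 3-point range-of-motion ratings do not suit this linear model, so state separately how they will be compared.
- Show the unadjusted independent-groups difference and CI alongside, and plot follow-up against baseline by arm so that an influential point or a weak correlation can be seen.
- Delete the between-arm baseline significance tests and present baseline values descriptively by arm.
- Data Analysis is written in the past tense. If the data have already been analysed, label the ANCOVA post hoc.

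**Cost.** New wording and a standard SPSS procedure on data already collected. Statistically it takes one residual degree of freedom (8 to 7) and fits a common slope to ten people, where one extreme baseline can drive the result. At zero correlation the interval is about 10% wider on average (1.55/1.41) and about 32% wider given a difference above 1 SD (1.86/1.41). At 0.5 it is about 14% wider given such a difference (1.61/1.41).

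### Independently randomised arms are compared by a separate paired t-test at each visit, a method that discards anyone missing a visit and, read literally, a measured person in the other arm

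*Combined protocol and SAP*

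**What the plan says.** In the combined protocol and SAP, Research Design and Participants, ten people "were randomly allocated to the OBI + TE ($n = 5$) or the TE ($n = 5$) group". The same section reports that "Two participants withdrew from the study prior to randomization" and gives no participant count beyond allocation. Outcomes Measures names the QuickDASH (0 to 100, lower is better): it says that this "questionnaire was the primary outcome measure". Under Procedure, "Outcome measures were administered prior to the intervention, a week after the conclusion of the intervention, and four weeks after the intervention ended", without saying how many people were measured at each time.

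Under Data Analysis, the between-arm comparison is: "Three sets of paired t-tests were used to compare the groups to each other at baseline, one week posttreatment, and four weeks posttreatment". The within-arm comparison is: "Paired sample t-tests were completed for each group for both the one week and four week follow up assessments". Significance is two-sided at 0.05. No model links the visits. No analysis population, statement that people are analysed as allocated, or rule for missing outcomes is given.

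**The concern.** Two features of the stated between-arm method work together.

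- **Pairing.** The arms are different people, allocated at random and not matched. A paired test needs a partner for each person, and here any pairing would be arbitrary, such as row order in the data file. It halves the degrees of freedom even when nobody is missing.
- **Separate visits.** A test at one visit can use only values from that visit. Someone seen at one week but not at four weeks drops out of the four-week test, although the one-week score is informative about the missing one. Under literal pairing, the partner in the other arm is dropped as well, despite having been measured.

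With five per arm, each person is 20% of the arm. If the person who missed a visit was the one doing badly, that arm would look better than it is, and the confidence interval would not show it.

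**Working it through.** **Inputs from the documents.** Participant flow from Research Design and Participants ("Eighteen older adults were recruited for the study, four did not meet the MMSE criteria, and two did not have a confirmed diagnosis", then two withdrawals before randomisation); five per arm; two follow-ups; two-sided alpha 0.05. No SD, effect size, between-visit correlation or miss rate is given, so results are in outcome SD units and the last two are assumed over a range.

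**Plan's own figure.** 18 − 4 − 2 − 2 = 10, which reproduces the number randomised. There is no power calculation to reproduce.

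**Cost of pairing with complete data** (zero correlation between arbitrary partners). The standard error is √(1/5 + 1/5) = 0.63 SD under either test. The difference lies in the critical value:
- independent, 5 v 5: df 8, t = 2.31, 95% half-width 2.306 × 0.632 = 1.46 SD;
- five pairs: df 4, t = 2.78, half-width 2.776 × 0.632 = 1.76 SD.

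**Cost of one missed visit.**
- Independent, 4 v 5: df 7, t = 2.36, half-width 2.365 × √(1/4 + 1/5) = 1.59 SD.
- Four pairs: df 3, t = 3.18, half-width 3.182 × √(2/4) = 2.25 SD.
- Power at an illustrative true difference of 1.5 SD (noncentral t): 55% (5 v 5), 49% (4 v 5), 44% (five pairs), 32% (four pairs).

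**Shift in the arm difference when one of five is lost** (independent reading). Losing a person d SD from the arm mean moves that mean by d/4, so 0.25 SD for d = 1 and 0.50 SD for d = 2.
- *Random loss:* the average shift is zero, its SD is √(1/4 − 1/5) = 0.22, and its mean absolute size is 0.18 SD. This is imprecision, not bias.
- *Outcome-related loss:* if the highest (worst) scorer at a visit is the one missing at that visit, simulation gives an average shift of −0.29 SD. If the worst one-week scorer misses four weeks, the shift scales with the correlation r between visits: 0.290 × r = 0.145, 0.203 and 0.232 SD at r = 0.5, 0.7 and 0.8. Direct simulation gives 0.145, 0.203 and 0.233 SD, in favour of the arm that lost the person. At r = 0.7 this is 0.20/0.63, about a third of a standard error.

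**Would a model using all visits help?** In the same scenario, a likelihood estimate with known covariance brings the average shift to about 0.00 SD at each correlation. The more realistic check is a three-visit REML model with compound symmetry: bias is 0.04 SD or less, root mean squared error at r = 0.7 falls from 0.688 to 0.643 SD, and null rejection stays at or below 5%. That check used 8 df rather than Satterthwaite df.

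**Chance of at least one absence among ten at a visit**, 1 − (1 − m)^10 for an assumed miss rate m: 1 − 0.95^10 = 40%; 1 − 0.90^10 = 65%; 1 − 0.80^10 = 89%.

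**The case against.** The strongest reply is that nothing here shows a missing outcome. The document describes a completed study, says that the measures were given at all three times, and reports withdrawals only before randomisation. Participants live where the clinic is located, which plausibly helps attendance. If all ten were measured, no mean shifts, and a saturated arm-by-visit model returns the same differences in means. This stands, and it makes the missing-data part of the point conditional.

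The bias figure is also one adverse scenario. Even there, an independent 4 v 5 test rejects a true null 5.6%, 6.2% or 6.6% of the time (r = 0.5, 0.7, 0.8), and a shift of about 0.2 SD is small beside a half-width of 1.46 SD. That is correct as to size. But the half-width expresses sampling error, whereas the shift has a direction that the interval does not reveal.

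Paired may simply be a slip for independent-samples. That would remove the loss of the partner, but the absent person would still be dropped.

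A reader might infer three stronger claims that the documents do not support:
- *That people were lost after randomisation.* No such loss is reported.
- *That the one-week and four-week results describe different people.* This needs someone to miss exactly one follow-up; a person missing both leaves the same group at each.
- *That loss was likely because 2 of the 12 eligible people withdrew.* Applying 2/12 to ten people gives 1 − (10/12)^10 = 84%, but it carries a pre-randomisation rate, resting on two events, over to a different kind of event.

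**Conclusion.** The point holds in a limited form. What does not depend on missing data is that a paired test between unmatched randomised arms is the wrong test. With all ten measured it leaves the difference in means unchanged but widens the 95% half-width from 1.46 to 1.76 SD, assuming zero correlation between arbitrary partners.

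The rest is conditional on a missed visit, which the documents do not show. If one occurred for reasons related to outcome, the complete-case difference could be off by about 0.15 to 0.23 SD against a standard error of about 0.63 SD. This assumes that one arm loses its worst one-week scorer at four weeks, with a correlation of 0.5 to 0.8. If loss was random, only precision suffers. The miss rates and correlations are assumptions, and so is the use of SD units.

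**What to change.** - Replace the per-visit between-arm paired tests with one repeated-measures model per continuous outcome: arm, visit and arm-by-visit, treating the arms as independent (SPSS MIXED, REML, Satterthwaite df, a simple covariance such as compound symmetry). Take the arm difference at each follow-up from that model.
- State that all ten are included in the arm to which they were allocated, and report the number measured per arm at each visit. If that is five and five throughout, the missing-data question is closed.
- If any QuickDASH value is missing, show the arm difference with it set to the best and then the worst observed score, as a descriptive range. Do not attach a rule that calls the finding robust when the direction holds: with one value missing and no true effect, such a rule is met about 64% of the time.

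The cost is a change of SAP wording and a short run in the package already named. The downside is that, with ten people, the model depends on a simple covariance structure and on missingness being explained by the observed scores. The best-to-worst range is there to show how much rests on that.

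### QuickDASH is the primary outcome but has no primary visit or comparison: two unranked between-arm tests at 0.05 carry about a 9% false-positive risk, not 5%

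*Combined protocol and SAP*

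**What the plan says.** Under Outcomes Measures, the QuickDASH "questionnaire was the primary outcome measure". The same section lists COPM performance and satisfaction, a functional test of four shoulder movements scored "using a 3-point scale for ROM and pain", grip strength and the NPRS.

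Procedure puts assessments at baseline, "a week after the conclusion of the intervention, and four weeks after the intervention ended". Neither follow-up is called primary.

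Data Analysis describes two kinds of test:

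- Within arms: "Paired sample t-tests were completed for each group for both the one week and four week follow up assessments".
- Between arms: "Three sets of paired t-tests were used to compare the groups to each other at baseline, one week posttreatment, and four weeks posttreatment".

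The section ends with a single threshold: "The statistical significance level was set at $p < 0.05$ (two-tailed". It does not mention QuickDASH, does not list which scores are tested, and gives no order, adjustment or primary comparison.

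**The concern.** Naming a primary outcome protects the error rate only if the analysis says which comparison, at which visit, carries the conclusion. Here the label stops at Outcomes Measures. A significant between-arm QuickDASH result at either follow-up could be presented as the primary finding, and nothing written prevents a significant secondary result from being presented in the same way.

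The title describes the trial as a study of effectiveness, and only ten participants were randomised. A lone p-value below 0.05 could therefore be given more weight than it can bear, and the stated 0.05 would not describe the error rate behind the conclusion.

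**Working it through.** The plan states no familywise error rate, power or sample-size calculation, so there is no figure of its own to reproduce beyond the per-test level of 0.05.

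**Inputs from the document**

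- Level per test: 0.05, two-sided (Data Analysis).
- Arms: 5 and 5 (Research Design and Participants).
- Between-arm tests per score: 3, of which 2 are after treatment (Data Analysis).
- Scores: QuickDASH 1, COPM 2, grip 1, NPRS 1, plus ROM (Outcomes Measures).

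**Assumed, because the document does not say**

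- ROM scoring. One summary score gives 1 + 2 + 1 + 1 + 1 = 6 scores. If ROM is not t-tested, or if COPM counts as one score, there are 5.
- Correlation between visits (0 to 0.9) and between outcomes (0 to 0.7).
- No true effect, normal data, and an independent-groups t-test with 8 degrees of freedom that holds its level. Using a paired test between independent arms is a separate issue.

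**Step 1: QuickDASH alone, two between-arm follow-up tests**

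If independent: 1 − 0.95² = 0.0975, or 9.75%. Simulated with 5 per arm (40,000 to 80,000 runs per setting):

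| Visit correlation | P(at least one p < 0.05) |
|---|---|
| 0 | about 10% |
| 0.5 | about 9% |
| 0.7 | 8% to 9% |
| 0.9 | about 7% |

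One visit named in advance would give 5%.

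**Step 2: any score at either follow-up**

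Between-arm follow-up tests: 5 × 2 = 10, or 6 × 2 = 12.

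If independent: 1 − 0.95¹⁰ = 0.401 and 1 − 0.95¹² = 0.460.

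| Correlation (outcomes / visits) | 10 tests | 12 tests |
|---|---|---|
| 0 / 0 | 40% | 46% |
| 0.3 / 0.5 | 36% | 41% |
| 0.5 / 0.7 | 31% | 35% |
| 0.7 / 0.7 | 26% | 28% |

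The range is 26% to 46% with both correlations at most 0.7. Raising the visit correlation to 0.9, with outcome correlation still 0.7, lowers it to about 22% for 10 tests and 25% for 12.

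**Step 3: does the form of t-test matter?**

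Repeating the simulation with a paired t-test between arms (4 degrees of freedom, arbitrary pairing of independent participants) gives 7% to 10% for QuickDASH and 27% to 46% for 12 tests. The conclusion does not turn on that choice.

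**The case against.** The strongest reply is that the plan does name a primary outcome, is titled a pilot, and never claims familywise control. Leaving secondary outcomes unadjusted beside a named primary is common, and the plan does not say that any significant outcome makes the trial positive. All of that stands. It confines the firm part of this point to QuickDASH, where the excess is from 5% to about 9%. It does not remove that excess, because two visits remain unranked. Nor does pilot status settle the matter, since the title also speaks of effectiveness and the plan sets a significance threshold.

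Three stronger readings are tempting, and the document does not support them:

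- **A false-positive risk of up to about 70%.** This needs each of the four movements to be t-tested separately for ROM and for pain: 1 + 2 + 8 + 1 + 1 = 13 scores, 26 between-arm follow-up tests, and 1 − 0.95²⁶ = 74% if independent. The document does not say that the eight ratings are tested separately. Data Analysis also provides frequencies and percentages for categorical variables, so the 3-point ratings may not be t-tested at all. Near-independence among movements of one shoulder is unlikely; outcome correlation 0.7 with visit correlation 0.7 gives 41%.
- **A burden of 42 to 91 tests.** At 7 tests per score (4 within-arm, 3 between-arm), 6 to 13 scores would give that total. It includes baseline comparisons, which cannot show an effect, and within-arm tests, which do not compare treatments. Neither enters the rates above.
- **About 25% on QuickDASH once its four within-arm tests are added.** This supposes no true change in either arm, although both arms received six weeks of active therapy. Reliance on within-arm tests is a separate question.

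**Conclusion.** The point holds, in limited form. As written, the plan leaves the primary outcome with two unranked between-arm tests and a false-positive risk of about 9% (7% to 10% over the assumed visit correlations). The 26% to 46% figure is conditional: it applies only if significance on any of 5 or 6 scores at either visit were taken as effectiveness, a rule that the plan neither states nor excludes. It would be higher only if the ROM and pain ratings were each t-tested.

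Both figures assume no true effect and valid independent-groups t-tests; the correlations are assumptions, not data from the document. Severity: should be fixed. The excess on the primary outcome is moderate, but the omission affects what the trial may conclude.

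**What to change.** Replace the blanket significance sentence in Data Analysis with wording such as:

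> The single confirmatory test is the between-arm difference in QuickDASH at [one named follow-up visit], two-sided 0.05. QuickDASH at the other follow-up and all COPM, ROM, grip and NPRS results are reported as between-arm estimates with 95% confidence intervals, without claims of statistical significance.

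Add a line saying how the ROM and pain ratings are scored, so that the set of reported results is known. No formal adjustment of the secondary outcomes is needed if no significance is claimed for them.

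The visit must have been chosen without sight of outcome data. The document is in the past tense and reports completed recruitment and allocation, but it does not say when the outcome data were examined. If they were seen before the visit was chosen, naming one now would not restore the 5% level. In that case, label every p-value exploratory and base no claim of effectiveness on any single p < 0.05.

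The edit is to wording only. Its cost is that an isolated p < 0.05 on a secondary outcome or at the other visit can no longer be reported as effectiveness; under the exploratory label, that extends to the QuickDASH test itself.

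### A pilot with five participants per arm is judged only by t-tests at p < 0.05, with no between-group estimate or confidence interval planned

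*Combined protocol and SAP*

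**What the plan says.** The title presents an effectiveness comparison and also calls the study "A Pilot Randomized Controlled Trial". Under Research Design and Participants, ten people "were randomly allocated to the OBI + TE ($n = 5$) or the TE ($n = 5$) group". Under Outcomes Measures, the QuickDASH "questionnaire was the primary outcome measure", and its scale is described: "Scores range from 0 to 100. A lower score indicates less disability".

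The Data Analysis section has three statistical components:

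- Summaries: "Descriptive statistics for all continuous variables included mean, standard deviation, and range", with frequencies and percentages for categorical variables.
- Within each arm, paired t-tests at both follow-ups, "to determine the effectiveness of the treatment protocol over time".
- Between arms: "Three sets of paired t-tests were used to compare the groups to each other at baseline, one week posttreatment, and four weeks posttreatment".

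It closes with the criterion: "The statistical significance level was set at $p < 0.05$ (two-tailed". The documents give no sample-size rationale, target difference, expected SD, effect size, between-group estimate or interval. They do not say how a significant or non-significant result will be worded.

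**The concern.** With no estimate or interval specified, the test verdict is the only planned between-arm inference. At 5 per arm that verdict carries little information. A benefit of a size usually called large will more often than not fail to reach p < 0.05, and a reader who sees only group summaries and a p-value may take this as evidence that the treatments are equivalent. When p < 0.05 is reached, the observed difference has had to be very big, so for most plausible true effects the estimate that accompanies the significant result is too large.

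A pilot is most useful for its estimated difference, the uncertainty of that estimate and the SD, because these feed the design of a full trial. The plan reports SDs but does not ask for the other two. An inflated difference carried forward would lead to an undersized next trial, and a misread null could stop one that was worth running.

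**Working it through.** The plan contains no power or precision figure, so there is none to reproduce.

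**Inputs from the documents.** 5 per arm (Research Design and Participants); two-sided α = 0.05 (Data Analysis); QuickDASH on a 0 to 100 scale (Outcomes Measures).

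**Assumptions.** Normal scores with equal SDs, no dropout, true differences of 0.5 to 2.0 SD, QuickDASH SD of 15 to 20 (wider range 10 to 25), and baseline correlations of 0.5 and 0.7. The between-arm test is taken as an independent-groups t-test on 8 df, because the document describes no matching of participants across arms.

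**1. Threshold for significance.** The standard error of the difference is SD × √(1/5 + 1/5) = 0.632 SD, and t(0.975, 8 df) = 2.306. The observed difference must therefore exceed 2.306 × 0.632 = 1.46 pooled SDs.

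**2. Power.** Non-central t on 8 df, with non-centrality d / 0.632. At d = 0.8, for example, this is 0.8 / 0.632 = 1.26.

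**3. Overstatement.** Mean absolute observed difference among significant results, divided by the true difference (1,000,000 simulated trials per value of d).

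| True difference (SD) | Power | Average overstatement when significant |
|---|---|---|
| 0.5 | 11% | 2.9× |
| 0.8 | 20% | 2.0× |
| 1.0 | 29% | 1.7× |
| 1.5 | 55% | 1.3× |
| 2.0 | 79% | 1.1× |

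Power reaches 50% at 1.41 SD and 80% at 2.02 SD.

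**4. Unadjusted interval.** The 95% half-width is 2.306 × 0.632 × SD = 1.46 SD.

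- SD 15: 1.458 × 15 = 21.9 points
- SD 20: 1.458 × 20 = 29.2 points
- SD 10 and SD 25: 14.6 and 36.5 points

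At SD 15, an observed difference of zero would leave about 22 points in either direction open.

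**5. Baseline-adjusted interval.** Adjustment leaves 7 df and reduces the residual SD by √(1 − r²), where r is the correlation between baseline and follow-up. Chance baseline imbalance takes back part of the gain, so the average half-width was simulated. The unadjusted average is 1.41 true SDs, slightly below 1.46 because the sample SD on 8 df averages about 0.97 of the true SD.

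| Baseline correlation | Adjusted half-width (SD) | At SD 15 | At SD 20 |
|---|---|---|---|
| 0.5 | 1.34 | 20.1 points | 26.8 points |
| 0.7 | 1.11 | 16.7 points | 22.2 points |

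Adjusted and unadjusted widths are about equal at a correlation of 0.4 (1.42 against 1.41 SD). With no correlation, adjustment is wider: 1.55 against 1.41 SD.

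**6. The tests as labelled.** If the between-arm tests were run as paired tests on arbitrary pairs (4 df, zero correlation), power would be lower: 9%, 17% and 23% at 0.5, 0.8 and 1.0 SD.

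**The case against.** Several stronger readings are tempting, and the documents do not support them.

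- A reader might infer that the plan equates non-significance with no difference. It sets a significance level and stops there. The misreading is likely, but it is not written down.
- A reader might infer that p < 0.05 always comes with an inflated estimate, or that large effects are generally missed. Neither is true without limits. At a true difference of 2 SD, power is 79%, average overstatement is 1.1 times, and more than a third of significant raw estimates do not exceed the truth. The documents give no expected effect, so where the truth lies in this range is unknown.
- A reader might infer that effectiveness will be concluded from the between-arm p-value. The word stands in the title and in the sentence on within-arm tests, and the documents contain no conclusion.

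The best objection to the remedy is that a 95% CI from the same t-test excludes zero exactly when p < 0.05, and adds no precision. The low power comes from N = 10 in a study already labelled a pilot. The interval is also only unmentioned: common software prints it, and if the descriptive summaries are given by arm, an unadjusted interval can be worked out by hand.

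These points limit the claim but do not remove it. An interval shows what the data leave open, which a verdict on one side of 0.05 does not. Whether that is reported should not depend on software output or the reader's arithmetic. The baseline-adjusted estimate is also a different analysis from the planned tests, and a more precise one when the baseline correlation exceeds about 0.4.

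**Conclusion.** The concern holds in this form: the plan rests its inference in a 5-per-arm pilot on t-tests at p < 0.05 and specifies no between-group estimate or interval. For true differences up to about 1.4 SD the rule fails to reach significance at least half the time. At 1 SD it fails 71% of the time (100% − 29%). Significant results overstate the raw difference on average, strongly at 0.5 to 1.0 SD and only slightly by 2 SD. The point figures rest on an assumed SD, and all figures rest on normal scores and a correct independent-groups test.

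This is a point about what is reported and how it is read. It is not a demand for more participants, and the change does not make five per arm conclusive. It should be made, but it does not invalidate the trial. Labelling the between-arm tests as paired is a separate error. It must be corrected in any case, since an interval built on arbitrary pairs would not be a sound estimate for independent arms.

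**What to change.** Replace the sentence on between-group paired t-tests and the significance sentence with wording such as:

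> For each outcome at one and four weeks after treatment, the result is the between-group difference (OBI + TE minus TE), adjusted for the baseline value of that outcome, with its 95% confidence interval and the residual SD. QuickDASH is reported first. P-values are exploratory. Neither effectiveness nor absence of a difference will be concluded from a p-value alone.

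The baseline comparison becomes descriptive, because baseline enters the model as a covariate.

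The cost is SAP wording and a standard linear model on data the plan already collects, with no extra participants or visits. There are three downsides. Adjustment uses one degree of freedom and widens the interval somewhat if the baseline correlation is below about 0.4. No headline significance claim can be made. The document is written in the past tense, so if results have already been seen, the revised analysis should be labelled as introduced afterwards.
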